7.2.4. Visit 2 – 2-Week Follow-Up Visit (14-17 Days After Visit 1)

If delivery occurs before this visit, this visit will not be conducted; however, the hematology and chemistry assessments planned to be collected at this visit should be conducted at the delivery visit, if possible. For the other procedures to be conducted at delivery, see Section 7.2.6.

- Ensure that the participant continues to be eligible for the study and meets none of the participant withdrawal criteria as described in Section 7.5.
- Measure vital signs, including weight, oral temperature, sitting blood pressure and pulse rate, and respiratory rate.
- Perform a targeted physical examination, evaluating any clinically significant
 abnormalities based on history and the participant's self-reported symptoms or
 complaints since the last visit. Abnormal results, including those that indicate
 worsening of medical history conditions, must be recorded on source documents
 and the AE CRF (with recording of time relative to vaccination) as appropriate.
- Perform obstetric examination including but not limited to fundal height, fetal heart tones, and fetal movement.
- Collect a blood sample of approximately 15 mL for immunogenicity assessments.
- Stage 2 sentinel cohort only: Obtain a blood sample (approximately 10 mL) for hematology and blood chemistry assessments. The following parameters will be assessed:
 - Hematology: hemoglobin, hematocrit, RBC count, WBC count with differential, and platelets.
 - Blood chemistries: ALT, AST, alkaline phosphatase, total bilirubin, BUN, and creatinine.
 - Retesting of abnormal laboratory parameters will be allowed at the discretion of the investigator if the investigator believes the results to be erroneous.
- Review the participant's e-diary data and collect the e-diary. Collect stop dates of any e-diary events ongoing on the last day that the e-diary was completed and record stop dates in the CRF.
- Complete the participant's source documents.
- Record nonstudy vaccinations and concomitant medications (including antibiotic medications) as described in Section 6.10.3.
- Record AEs as described in Section 8.8 and Section 9.
- The investigator or an authorized designee completes the CRF.

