8.5.1. Participant Electronic Diary

The participant will be asked to monitor and record local reactions, systemic events, including fever, and antipyretics/pain medication used to prevent and/or treat symptoms, within a fixed time window each day for 7 days following vaccination (where Day 1 is the day of vaccination) on a system that uses a personal digital assistant (PDA) or other technology. In Stages 2 and 3, a baseline assessment (nausea/vomiting, diarrhea, headache, fatigue/tiredness, muscle pain, or joint pain over the previous month) prior to vaccination will be recorded in the e-diary. This system, hereafter referred to as the participant's e-diary, allows recording of these assessments only within a fixed time window, thus providing the accurate representation of the participant's experience at that time. Data on local reactions, systemic events, and antipyretics/pain medication used to prevent and/or treat symptoms reported on the e-diary will be transferred electronically to the e-diary vendor, where they will be available for review by investigators, their qualified designees, and sponsor staff at all times via an internet-based portal. At intervals agreed to by the vendor and Pfizer, these data will be transferred electronically to Pfizer for analysis and reporting. These data do not need to be reported by the investigator in the CRF. However, if a participant withdraws because of prompted events reported in the e-diary, the event(s) should be recorded on the AE page of the CRF, regardless of whether the investigator considers the event(s) to be clinically significant.

Investigators (or appropriately qualified designee) are required to review the e-diary data online to evaluate participant compliance and as part of the ongoing safety review (see Stopping Rules in Section 8.7).

The investigator or designee must contact the participant in order to obtain stop dates for any reactions ongoing on the last day that the e-diary was completed. The stop dates should be documented in the source documents and the information entered in the CRF.

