8.5.2.1. Local Reactions

From Day 1 to Day 7, where Day 1 is the day of vaccination, participants will be asked to assess pain at the injection site, redness, and swelling and to record the symptoms in the e-diary in the evening. Redness and swelling will be measured and recorded in measuring device units (range: 1 to 21+), and then categorized during analysis as mild, moderate, or severe based on the grading scale in Table 4 below. Measuring device units can be converted to centimeters according to the following scale: 1 measuring device unit = 0.5 cm. Pain at the vaccine injection site will be assessed by the participant as mild, moderate, or severe according to the grading scale in Table 4 below. A participant with a severe (Grade 3 or above) local reaction will be prompted to contact the investigator to perform an unscheduled visit and assess the reaction.

Only an investigator can classify a participant's local reaction as Grade 4, after physical examination of the participant or documentation from another medically qualified source (eg, emergency room or hospital record), or, in the case of pain at the injection site only, telephone contact with the participant. If a participant experiences a Grade 4 local reaction, the investigator must immediately notify the sponsor. Site staff will educate the participant regarding signs and symptoms that would prompt site contact. The procedure for notification of the sponsor is provided in the study documentation.

If a local reaction persists beyond the end of the e-diary period following vaccination, the participant will be requested to report that information and/or any new AEs that develop to the investigator. The investigator will enter this additional information in the CRF.

	Mild (Grade 1)	Moderate (Grade 2)	Severe (Grade 3) ^a	Grade 4 ^b
Pain at injection site	Does not interfere with activity	Repeated use of nonnarcotic pain reliever >24 hours or interferes with activity	Any use of narcotic pain reliever or prevents daily activity ^c	Emergency room visit or hospitalization
Erythema/ Redness	2.5 cm to 5.0 cm (5 to 10 measuring device units)	>5.0 cm to 10.0 cm (11 to 20 measuring device units)	>10 cm (≥21 measuring device units)	Necrosis or exfoliative dermatitis
Induration/ Swelling	2.5 cm to 5.0 cm (5 to 10 measuring	>5.0 cm to 10.0 cm (11 to 20 measuring device units)	>10 cm (≥21 measuring device units)	Necrosis

Table 4. Local Reaction Grading Scale

device units)

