## Duration of Each Local Reaction

The duration of each local reaction will be calculated in days as (resolution date of reaction – start date of reaction + 1). Resolution of the event is the last day on which the event is recorded in the e-diary or the date the event ends if it is unresolved during the participant diary-recording period (end date collected on the CRF), unless chronicity is established. If there is no known end date, the duration will be considered unknown and set to missing. Participants with no reported reaction have no duration.

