The derivation of these variables is similar to the derivation of the variables for local reactions (Section 3.6.2.1). Any systemic event includes fever, nausea/vomiting, diarrhea, headache, fatigue/tiredness, muscle pain, or joint pain.

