## 6.7.2. Reactogenicity Data

The derived endpoints (Section 3.6.2) for each local reaction, systemic event, and use of antipyretic/pain medication will be summarized.

Additionally, for the baseline assessment of systemic events collected on Day 1 for maternal participants (Stages 2 and 3), the number and percentage of participants with individual systemic events along with the corresponding 2-sided 95% CIs will be displayed separately, by vaccine group.

The number and percentage of participants with individual local reactions and any local reaction will be summarized on each of Days 1 through 7 separately. Two (2)-sided 95% CIs will also be displayed. A similar set of outputs may be produced combining reactions that are moderate or severe in grade. Similar analysis will be repeated for each systemic event and any systemic event.

For the maximum duration of local reactions, systemic events, and use of antipyretic/pain medication, descriptive summary statistics will be provided separately.

For the onset (day) of local reactions, systemic events, and use of antipyretic/pain medication, descriptive summary statistics will be provided separately.

The maximum reported diameters for redness and swelling will be summarized using descriptive statistics, by vaccine group.

A participant data listing will be provided for all reactogenicity data and for participants experiencing severe redness or swelling.

All summaries and listings for the reactogenicity data will be generated separately for nonpregnant women receiving the primary and booster vaccinations (Stage 1) and maternal participants (Stages 2 and 3).

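### Reactions without a known end date are set to missing and not counted, so the reported mean and maximum reaction duration can be understated, probably by a small amount

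*SAP*

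**What the plan says.** SAP 3.6.2.1 (Duration of Each Local Reaction) computes duration in days, inclusive of the first and last day. The end is either the last diary day on which the reaction is recorded or "the date the event ends if it is unresolved during the participant diary-recording period (end date collected on the CRF), unless chronicity is established". It then states: "If there is no known end date, the duration will be considered unknown and set to missing". SAP 3.6.2.2 and 3.6.2.3 derive the corresponding variables for systemic events and medication use in the same way.

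SAP 6.7.2 plans the display: "For the maximum duration of local reactions, systemic events, and use of antipyretic/pain medication, descriptive summary statistics will be provided separately". Under SAP 5.2 the default statistics are n, mean, median, standard deviation, minimum and maximum. SAP 5.3.2.1 rules out imputing reactogenicity data beyond what 3.6.2 describes.

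The protocol limits how often an end date should be unknown. Section 8.5.1 puts a duty on the investigator (or a delegate), who "must contact the participant in order to obtain stop dates for any reactions ongoing on the last day that the e-diary was completed". At Visit 2 for maternal participants (7.2.4) the instruction is: "Collect stop dates of any e-diary events ongoing on the last day that the e-diary was completed and record stop dates in the CRF". The same step stands at Stage 1 Visit 2 (7.1.3) and at booster Visit 7 (7.1.8). Section 8.5.2.1 adds: "If a local reaction persists beyond the end of the e-diary period following vaccination, the participant will be requested to report that information", and the investigator enters it in the CRF.

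**The concern.** Whether a duration is missing depends on the duration itself. A reaction seen to end within the diary can never be missing; a reaction still present when last observed can be. Removing only reactions of the second kind leaves a summary of durations among reactions that were seen to end, which is not the same as durations among all reactions.

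The clearest case is a chronic reaction. The SAP exempts it from the CRF end-date rule but gives it no other value, so as written it probably has no end date and leaves the table. A vaccine group with one never-resolving reaction could then show a maximum of a few days, with nothing in the duration table to signal the omission. With 22 participants per group in Stage 1 and 40 per GBS6 group in Stage 2, a single omitted event can change a group's mean and maximum.

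**Working it through.** **Which reactions lose their duration.** From SAP 3.6.2.1:

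1. Ends within the completed diary: the last recorded day is the end; duration always known.
2. Ongoing at the last completed diary day, stop date on the CRF: full duration kept.
3. Ongoing at the last completed diary day, no stop date obtained: missing.
4. Chronicity established: no value specified; probably missing.

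Only cases 3 and 4 are dropped. Each has a known lower bound, the last diary day with the reaction minus the start day plus one.

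**Direction.** Let p be the share of reactions with missing duration. Then

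full mean − reported mean = p × (mean of missing − mean of reported).

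Dropped reactions were all ongoing when last seen, so they tend to be longer than average and the difference tends to be positive. The reported maximum can only equal the true maximum or fall below it.

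**Size.** The documents state no durations, no share ongoing after Day 7 and no share of unknown end dates, so there is no plan figure to reproduce. Everything below is assumed.

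From the formula with a reported mean of 2 days: 1% missing with mean 10 days gives 0.01 × (10 − 2) = 0.08 day; 5% missing with mean 14 days gives 0.05 × (14 − 2) = 0.60 day.

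A simulation used geometric durations with mean 2 or 3 days and onset on Day 1 (80%) or Day 2 (20%), with either no long tail or 2% of reactions lasting 8 to 60 days. Diaries were complete, and u is the share of reactions past Day 7 with no stop date. Cells show the mean with all end dates known, the mean under the SAP rule, and the difference in days.

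| Mean; tail | Past Day 7 | u = 10% | u = 25% | u = 100% |
|---|---|---|---|---|
| 2; none | about 1% | 2.002, 1.996 (0.006) | 1.999, 1.982 (0.017) | 2.002, 1.938 (0.064) |
| 3; none | about 6% | 3.003, 2.958 (0.045) | 3.003, 2.892 (0.111) | 3.008, 2.538 (0.470) |
| 2; 2% | about 3% | 2.627, 2.560 (0.067) | 2.651, 2.474 (0.177) | 2.655, 1.938 (0.717) |
| 3; 2% | about 8% | 3.624, 3.523 (0.101) | 3.628, 3.372 (0.256) | 3.617, 2.533 (1.084) |

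The last cell agrees with the formula: 0.083 × (15.574 − 2.533) = 1.08. The u = 100% column is an outer limit in which stop-date collection fails every time.

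For the maximum, take 43 reactions in a group (an assumed 40% of 108) and mean 2 days. The chance that the reported maximum is too low is 1.6% to 8.1% without the tail and 3.4% to 17.7% with it, for u from 5% to 25%. At u = 100% it is 32.6% and 71.3%.

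**One persistent reaction in a small group.** Assume 20 reactions: 19 average 2.5 days and one is still ongoing after 30 days. The SAP rule reports 2.5. With 30 days as the lower bound the mean is (19 × 2.5 + 30)/20 = 3.875. If only the diary date is available, the bound is at most 7 days and the mean is (47.5 + 7)/20 = 2.725. The reported maximum omits the event in either case.

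**The case against.** The strongest reply is that the plan already does most of what is needed. Stop-date collection is mandatory, SAP 3.6.2.2 says that systemic events ongoing on Day 7 get a CRF stop date, and Protocol 8.5.2.3 has a Day 7 fever measured daily until it resolves. Long reactions with a stop date stay in. A dropped reaction still counts for presence and maximum severity, and SAP 6.7.2 lists all reactogenicity data. The duration table shows n, so the number without a duration can be found by subtracting it from the number with the reaction.

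Most of this stands, and it is why the effect is probably small. It does not close the gap. The scheduled stop-date step for maternal participants is 14 to 17 days after vaccination. A reaction still present then has no stop date to give, and the Visit 3 procedures (Protocol 7.2.5) name no such step. If delivery comes before Visit 2, that visit is not held and the delivery procedures (7.2.6) name no diary review; only the general duties in 8.5.1 and 8.5.2 remain. The SAP evidently expects some unknown end dates, since it writes a rule for them. Subtraction gives a count but does not separate chronic reactions from lost contacts, and it leaves the mean and maximum as they are.

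It is also fair to say that Kaplan-Meier medians for three local reactions, seven systemic events and medication use across up to seven groups would be more than this supportive summary needs.

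**Conclusion.** The concern holds in a limited form. Cases 3 and 4 above leave the duration summaries with no planned count, censoring or lower bound, so mean and maximum duration can be understated. The documents do not allow the amount to be estimated; given the required stop-date collection it is probably small. The treatment of chronic reactions rests on a reading of text that is not explicit.

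A reader might infer more than this, in four ways.

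- That the longest reactions are, as a rule, the ones removed. The CRF end date in the same SAP paragraph contradicts this. Nor is a dropped reaction necessarily long: a participant who stops the diary on Day 3 with an ongoing reaction and gives no stop date is dropped too.
- That the bias is large. If 5% to 20% of all reactions lacked an end date and averaged 10 days against 2.5 for the rest, the full mean would be 2.875 to 4.0 days and the reported 2.5 would be 13% to 38% too low. Those shares have no source. With geometric durations of mean 2.5 days and onset on Day 1, only 0.6^7 = 2.8% of reactions would outlast Day 7.
- That vaccine-placebo differences are narrowed. This would need unresolved reactions to be more common after vaccine, and no between-group comparison of duration is planned.
- That the primary safety results are affected. The reactogenicity endpoints are proportions, analysed by maximum severity (SAP 6.1.1 and 6.1.2); duration appears only in the supportive summaries of 6.7.2.

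**What to change.** In SAP 3.6.2.1, carried to 3.6.2.2 and 3.6.2.3, replace the set-to-missing rule. A reaction without an end date, including one judged chronic, is kept as censored at the last date on which it was recorded as ongoing, which is at least the last diary day reported.

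In SAP 6.7.2, report by vaccine group the number of reactions with an unknown or unresolved end. Show the maximum as ≥ x days when the longest is unresolved, and add a sensitivity summary that uses the lower-bound durations. A Kaplan-Meier median is optional.

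The cost is a short change to the SAP text and one or two extra rows in an existing table, and the reported durations become slightly longer. No new data are needed for the minimum version, because the diary date always exists. Where the CRF holds no later date, the lower bound cannot exceed 7 days, and the table should say so.

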## Onset of Local Reaction

The onset day of each local reaction and any local reaction will be derived.

For the onset day of each local reaction, if participants report severity change of the local reaction, the first day of initial reporting of that specific local reaction will be counted.

For the onset day of any local reaction, the first day of reporting any severity of any local reaction will be counted.

In summary, the following variables will be derived for local reactions:

- Presence or absence of each local reaction on each day (Days 1-7) after vaccination.
- Presence or absence of each local reaction on "any day (Day 1-7)" after vaccination.
- Maximum severity of each local reaction on "any day (Day 1-7)" after vaccination.
- Presence or absence of any local reaction on "any day (Day 1-7)" after vaccination.
- Duration of each local reaction after vaccination.
- Onset day of each local reaction after vaccination.
- 7. Onset day of any local reaction after vaccination.

#### 3.6.2.2. Systemic Events

In addition to data from Days 1 through 7 for all nonpregnant women (Stage 1 – primary and booster vaccinations separately) and maternal participants (Stages 2 and 3), prior to vaccination on Day 1, a baseline assessment of systemic events will be recorded in the e-diary for the maternal participants (Stages 2 and 3).

Systemic events reported via e-diary are: fever, nausea/vomiting, diarrhea, headache, fatigue/tiredness, muscle pain, and joint pain. The highest temperature for each day for 7 days after vaccination is recorded in the e-diary. The protocol defines fever as an oral temperature >38.0°C (≥100.4°F). For ongoing fever on Day 7, the stop date will be recorded in the CRF. Additionally, the participant is to document the presence or absence of remaining systemic events in the e-diary as 'Mild', 'Moderate', 'Severe', or 'None'. Participants are asked to assess the severity of each event according to Table 5. Study staff may also contact the participant to obtain additional information on Grade 3 events entered into the e-diary. Only an investigator is able to classify a participant's systemic event as Grade 4, after physical examination of the participant or documentation from another medically qualified source (eg, emergency room or hospital record), or telephone contact with the participant. If a participant experiences a Grade 4 systemic event, it will be captured under the unplanned visit CRF page. A severe systemic event entry in the e-diary that later is assessed as Grade 4

will be treated as Grade 4 for analyses. For all ongoing systemic events on Day 7, the stop date will be recorded in the CRF.

Any temperature recorded as <35.0°C (<95.0°F) or >42.0°C (>107.6°F) will be treated as data entry errors and excluded from the analyses. For reporting purposes, fever will be analyzed using the following temperature ranges:

- ≥38.0°C to ≤38.4°C (≥100.4°F to ≤101.1°F)
- ≥38.5°C to ≤38.9°C (≥101.2°F to ≤102.0°F)
- ≥39.0°C to ≤40.0°C (≥102.1°F to ≤104.0°F)
- >40.0°C (>104.0°F)

Table 6. Systemic Events Grading Scale

	Mild (Grade 1)	Moderate (Grade 2)	Severe (Grade 3) a	Grade 4 b
Nausea/vomiting	No interference with activity or 1-2 times in 24 hours	Some interference with activity or >2 times in 24 hours	Prevents daily activity; requires IV hydration	Emergency room visit or hospitalization for hypotensive shock
Diarrhea	2-3 loose stools in 24 hours	4-5 loose stools in 24 hours	≥6 loose stools in 24 hours	Emergency room visit or hospitalization
Headache	No interference with activity	Repeated use of nonnarcotic pain reliever >24 hours or some interference with activity	Significant; any use of narcotic pain reliever or prevents daily activity c	Emergency room visit or hospitalization
Fatigue/tiredness	No interference with activity	Some interference with activity	Significant; prevents daily activity c	Emergency room visit or hospitalization
Muscle pain	No interference with activity	Some interference with activity	Significant; prevents daily activity c	Emergency room visit or hospitalization
Joint pain	No interference with activity	Some interference with activity	Significant; prevents daily activity c	Emergency room visit or hospitalization

Abbreviations: CRF = case report form; IV = intravenous.

- Participants experiencing ≥ Grade 3 systemic events are to be seen by the study site.
- b. Grade 4 assessment should be made by the investigator. Grade 4 events will not be collected in the e-diary but will be recorded as AEs on the CRF.
- Prevents daily routine activity, ie, results in missed days of work or school or is otherwise incapacitating
  or includes use of narcotics for analgesia.

The presence or absence of each systemic event on a given day is defined as follows:

- = missing, if value is missing on a given day,
- = 'Yes', if the participant reports a temperature ≥38.0°C (≥100.4°F) for fever or fever is assessed as 'Mild', 'Moderate', 'Severe', or 'Grade 4' for the remaining events on a given day,
- = 'No', if the participant reports a temperature <38.0°C (<100.4°F) for fever or 'None' for the remaining events on a given day.

For each systemic event, the following variables will be derived:

- Presence or absence of each systemic event on each day (up to Day 7) after vaccination.
- Presence or absence of each systemic event on "any day (Day 1-7)" after vaccination.
- Maximum severity of each systemic event on "any day (Day 1-7)" after vaccination.
- Presence or absence of any systemic event on "any day (Day 1-7)" after vaccination.
- Duration of each systemic event after vaccination.
- Onset day of each systemic event after vaccination.
- Onset day of any systemic event after vaccination.

The derivation of these variables is similar to the derivation of the variables for local reactions (Section 3.6.2.1). Any systemic event includes fever, nausea/vomiting, diarrhea, headache, fatigue/tiredness, muscle pain, or joint pain.

